For continuous secondary outcomes, groups will be compared for differences at the 1-year follow-up using the same analytic approach specified for the primary outcome. For binary secondary outcomes, either logistic regression or Poisson regression with robust error variance will be employed, depending on whether the outcome is rare or common. For categorical outcomes, either ordinal or multinomial logistic regression models will be utilized, depending on the nature of the measure and empirical tests of the proportional odds assumption.

Statistical significance for the primary outcome will be defined as p < 0.05. Secondary outcomes will be evaluated for statistical significance with a Hochberg modification to the Bonferroni adjustment, in which the p-values of the five outcomes will be ordered. The largest p-value will be compared relative to p < 0.05, and if met, all parameters will be considered significant. If not, then the second largest p-value will be assessed relative to p < 0.05/2 = 0.025, and if met, then it and all other parameters will be considered significant, and so on for the third p-value at p < 0.05/3 = 0.017.

12 Data management

Trained data management and study management staff at the UNC CSCC will be responsible for coordinating data management. The Coordinating Center (CC) uses a customized state-of-the-art web-based data management system using Carolina Data Acquisition and Reporting Tool (CDART) which is also used for the parent ACHIEVE study and ARIC-NCS. A complete description of all data management procedures has previously been developed for the parent ACHIEVE trial and has been approved by the ACHIEVE DSMB. CDART uses a flexible, secure authentication system requiring a username and password. In accordance with HIPAA, all individually identifiable information is encrypted and decrypted for local on-screen display at field sites. The GrandPad tablet is HIPAA-compliant with respect to any telehealth sessions that occur using this platform.

Data collection

The CC has previously led the translation of the protocol data collection specifications into a consolidated set of clear, unambiguous electronic case report forms (eCRFs) for the parent ACHIEVE trial. Each eCRF has a corresponding paper form to be used by sites in cases where data cannot be entered at the time of collection.

Randomization and blinding

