7.7 Adjustment for Multiple Comparisons

Statistical significance for the primary outcome will be defined as $p < 0.05$. Secondary outcomes will be evaluated for statistical significance with a Hochberg modification to the Bonferroni adjustment, in which the p-values of the five outcomes will be ordered. The largest p-value will be compared relative to $p < 0.05$,

and if met, all parameters will be considered significant. If not, then the second largest p-value will be assessed relative to $p < 0.05/2 = 0.025$, and if met then it and all other parameters will be considered significant, and so on for the third p-value at $0.05/3=0.017$.

8. Software and Statistical Programming

Tabulations and statistical analyses will be performed using SAS® Version 9 (or later). All programming will be done by the ACHIEVE DCC which is housed in the Collaborative Studies Coordinating Center (CSCC) at the University of North Carolina at Chapel Hill. Standard CSCC statistical computing procedures will be followed. That is, research staff will submit a written statistical computing request to the statistical programming staff. A computing request number will be assigned to the request and information about the request entered into a database. A statistical programmer will then be assigned to undertake the request. Statisticians will review the programs and output. If necessary, changes will be requested in writing. After the programming has been completed to the satisfaction of the staff, all materials will be archived under the request number. Archived materials will include the original computing request, any subsequent changes, the SAS® code as well as any output, including log and list files and datasets created in the request.

9. References

- [1] American Speech Language Hearing Association , "Preferred Practice Patterns for the Profession of Audiolog," *Rockville, MD*, 2006.
- [2] Audiology Australia, "Audiology Australia Professional Practice Standards – Part B: Clinical Standardsle," *Forest Hill, Victoria*, 2013.
- [3] British Society of Audiology, "Practice Guidance: Common Principles of Rehabilitation for Adults in Audiology Services," *Bathgate, UK*, 2016.
- [4] J. H.-Y. Ng and A. Y. Loke, "Determinants of hearing-aid adoption and use among the elderly: A systematic review," *Int J Audiol*, vol. doi: 10.3109/14992027.2014.966922, pp. 1-10, 2015; 2027 (April 2014).

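### The written Hochberg rule does not limit rejection to smaller p-values, so read literally it declares significant a secondary outcome that has just failed its own cut-off

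*SAP*

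**What the plan says.** SAP 7.7 (Adjustment for Multiple Comparisons) names the method: "Secondary outcomes will be evaluated for statistical significance with a Hochberg modification to the Bonferroni adjustment". The p-values are ordered and the largest is compared with 0.05; "and if met, all parameters will be considered significant". If it fails, the second largest is compared with 0.05/2 = 0.025, and the consequence is stated as "if met then it and all other parameters will be considered significant, and so on for the third p-value", with a cut-off of 0.05/3 = 0.017 for the third.

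Protocol 11.2 (Analytic approach) carries the same rule: "and if met, then it and all other parameters will be considered significant, and so on for the third p-value".

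Neither document says which side of the ordering the other parameters lie on, or that an outcome which has failed its step stays non-significant. SAP 7.5 and Protocol section 3 list three secondary outcomes: the IOI-CHI satisfaction item, the COSI primary-goal item and the HHIE-S score.

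**The concern.** In Hochberg's step-up procedure, an outcome that fails its step is not rejected. When a later step passes, the outcome at that step and those with smaller p-values are rejected. Step 2 exists here only because the largest p-value has failed, so every outcome apart from the second largest includes the one that failed. The literal sentence brings that outcome back. The phrase 'and so on' can carry the same consequence to step 3, where one p-value below 0.017 would make all three outcomes significant, although Hochberg allows only the smallest at that step.

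At stake is familywise error control for the secondary claims. The two readings agree when no outcome has a real effect. They part when telehealth improves some outcomes and not others.

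**Working it through.** **Reproducing the plan's cut-offs.** 0.05/1 = 0.0500, 0.05/2 = 0.0250 and 0.05/3 = 0.0167, printed as 0.017. All three match Hochberg's.

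**An example.** Take p = 0.60, 0.020, 0.010.
- Step 1: 0.60 is not below 0.05, so it fails.
- Step 2: 0.020 is below 0.025, so it passes.
- Hochberg declares the outcomes with 0.020 and 0.010. The literal sentence also declares the one with 0.60.

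**Size if applied literally.** The documents give no effect sizes, correlations or sidedness for the secondary outcomes, so these are assumptions: three two-sided tests, normal test statistics, pairwise correlation 0, 0.3 and 0.5, and each real effect with 80% power at 0.05 (mean z = 1.960 + 0.842 = 2.802). With 400,000 draws per scenario, the chance of declaring at least one null outcome significant is:

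| Real effects / nulls | Hochberg | Literal at step 2 only | Literal at steps 2 and 3 |
|---|---|---|---|
| 0 / 3 | about 5% | same as Hochberg | same as Hochberg |
| 1 / 2 | 4-5% | same as Hochberg | about 67% |
| 2 / 1 | about 4% | 52-58% | 82-89% |

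**Hand check at correlation 0.**
- Two real effects, step 2 only. If both real outcomes have p < 0.025, step 1 or step 2 must pass, and the literal rule declares the null. Each does so with probability Φ(2.802 − 2.241) = Φ(0.561) = 0.712, and 0.712² = 0.507. This is a lower bound; the simulation gives 0.52.
- Two real effects, steps 2 and 3. Any p-value below 0.0167 is enough. For one real outcome the chance is Φ(2.802 − 2.394) = Φ(0.408) = 0.658. For at least one of two it is 1 − (1 − 0.658)² = 0.883, again a lower bound; the simulation gives 0.89.
- One real effect, steps 2 and 3. The lower bound is 0.658; the simulation gives 0.67.

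**Why two cells do not change.** With one real effect and two nulls, passing step 2 means that the two smallest p-values are both below 0.025. At least one of them belongs to a null outcome, which Hochberg would already have rejected. The literal wording at step 2 may add the second null, but it does not raise the chance of at least one false declaration. With three nulls, any passing step is already a false declaration under both readings.

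**Sensitivity to assumed power.** With two real effects at 50% power each, the literal wording at both steps declares the null in 57%, 52% and 48% of trials at correlation 0, 0.3 and 0.6, against about 3% under Hochberg.

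**The case against.** The strongest reply is that the paragraph defines its method by name. Hochberg's procedure is a settled rule, the order and all three cut-offs are its own, and a statistician told to run it would leave the failed outcome unrejected. The wording itself gives some support: step 1 speaks of all parameters, while step 2 changes to the passing one and all others, which fits a list being worked through with the failed outcome already set aside. On the literal reading, failing a step would cost the failed outcome nothing once a later step passed, which defeats the purpose of the adjustment. The two documents carry nearly the same sentence, so the repetition is one drafting slip copied, not separate evidence of intent. SAP section 8 also has statisticians review programs and output.

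Most of this stands. A reader might infer that the trial plans an invalid multiplicity test, or that its secondary claims carry a false-positive rate of 52-89%. The documents do not support either inference. They name a valid procedure, and those percentages describe what would follow if the clause were programmed against the named method, under assumed effects.

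What the reply does not do is correct the sentence. It is the step-by-step specification, and on this one consequence it conflicts with the method it names. Neither reference list cites a source for the Hochberg procedure, and no worked example or code settles the conflict. Program review makes a literal implementation less likely, but the reviewer would be checking against text that permits it.

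**Conclusion.** The consequence written at step 2, and by extension at step 3, does not match the Hochberg procedure named in the same paragraph. Standard Hochberg is the likely intent, but the text allows two readings that can give different claims from the same p-values.

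Applied literally to three outcomes, the rule loses familywise control when two outcomes have real effects (52-58% or 82-89%, against about 4%). It also does so when one has a real effect, but only if the wording carries to step 3 (about 67% against 4-5%). With no real effects nothing changes. These sizes rest on assumed 80% power, correlation of 0 to 0.5 and two-sided tests; the mismatch itself rests on no assumption.

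The primary outcome, tested separately at 0.05, is unaffected. This is a low-cost correction to the secondary-outcome decision rule and does not put the validity of the trial in question.

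**What to change.** In SAP 7.7 and Protocol 11.2, replace the consequence at step 2 with: *it and all outcomes with smaller p-values will be considered significant; outcomes with larger p-values will not*. State that the same applies at step 3, so that with three outcomes only the one with the smallest p-value can be declared significant there. Under that rule the simulated familywise error was at or below about 0.05 in every scenario run.

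The cost is one sentence in each document, with no effect on data collection, and it should be made before secondary results are declared. The same paragraph orders five outcomes where three are listed. That is a separate point, but it is convenient to settle it in the same edit, because with five outcomes the cut-offs 0.05/4 = 0.0125 and 0.05/5 = 0.01 would also have to be written out.
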